7.4.9. The Functional Activities Questionnaires (FAQ)

The Functional Activities Questionnaire (FAQ) measures instrumental activities of daily living (IADLs), such as preparing balanced meals and managing personal finances. Since functional changes are noted earlier in the dementia process with IADLs that require a higher cognitive ability compared to basic activities of daily living (ADLs) this tool is useful to monitor these functional changes over time.

7.4.10. Animal Naming

Animal Naming is a word fluency test measuring executive functioning and language ability. The subject is asked to list all of the animals he/she can think of in the next 60 seconds.

7.4.11. Wechsler Memory Scale Logical Memory

The Wechsler Memory Scale (WMS) is a neuropsychological test designed to measure different memory functions in a person. Logical memory represents one of 7 memory subtests that are included within the WMS-IV. Of all the subtests, logical memory is the largest discriminator between the normal aging population and mild dementia (50). Subjects are read two thematically independent stories and later asked to recall each story immediately and later thirty minutes after the reading. Patients struggling with recall of story contents are provided cues to assist with recognition.

7.4.12 Alberta Smell Test

The Alberta Smell Test (AST) is a quick, easy to use method to test the ability to identify smells presented to one nostril at a time (51). Over the course of the test, the subject is presented with 8 different odors of the [name] scented markers namely, licorice, cinnamon, mint, orange, lemon, grape, melon, and raspberry. In 20 trials, the different scented markers are held up to the participants’ right or left nostril with their eyes closed. The subjects then select the scent of the marker from a list of the 8 scents. Each smell correctly identified will be recorded as a correct response with a maximum score of 20. A score of 2/10 or less in either nostril suggests impairment.

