Clinical trials of intranasal insulin in AD have demonstrated therapeutic effects involving memory, attention and cognition without significantly altering serum insulin or glucose levels. A clinical trial consisting of 26 memory impaired subjects (13 with AD and 13 with mild cognitive impairment) and 35 normal controls showed that IN insulin 20 IU or 40 IU resulted in improvements on two declarative memory tasks compared to placebo within 15 minutes of drug administration (29). IN insulin administered at 20 IU resulted in greater story recall whereas doses at 40 IU more favorably improved word list recall. There was no impact on IN insulin on serum glucose or insulin levels. Another study of 24 early AD/mild cognitive impairment subjects showed that 20 IU BID of intranasal insulin resulted in sustained benefit in over a 21 day period (30). Furthermore, IN insulin induced favorable changes in the serum amyloid-beta 40/42 ratio while having no impact on systemic glucose or insulin levels. Most recently, Craft and colleagues have shown improved memory and function as represented by the ADAS-Cog and ADCS-ADL, respectively in AD patients treated during a four month clinical trial (31). These changes in memory and function were associated with favorable changes in CSF tau and tau-Ab42 ratio. Additionally, IN insulin minimized progression in loss of cerebral hypometabolism as measured by FDG-PET.

Therapeutic response to IN insulin may be modified by both insulin type as well as ApoE4 carrier status. A study of 38 normal subjects showed that rapid-acting insulin aspart (Insulin NovoLog HM, Novo Nordisk) resulted in greater declarative memory improvements compared to regular insulin over 8 an week period (32). Additional clinical trials have suggested memory benefits associated with IN insulin are diminished among ApoE4 carriers diagnosed with AD (29).

Glulisine is a rapidly absorbed insulin analogue lacking the zinc ingredient commonly found in insulin formulations. This analogue differs from human insulin in that the amino acid asparagine at position B3 is replaced by lysine and the lysine in position B29 is replaced by glutamic acid. For this study, we have chosen glulisine due to prior speculation that zinc-containing compounds may be toxic to olfactory neurons (33, 34) as well as prior studies demonstrating improvements in declarative memory with RA compared to regular insulin.

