2.1. Pressurized Olfactory Delivery (POD) Device

The Pressurized Olfactory Delivery (POD) device is intended to be used with a variety of known and yet-to-be-known drugs. The POD device is designed specifically to deliver centrally acting drugs via the olfactory and trigeminal neural pathways in the roof of the nasal cavity and olfactory nasal epithelium.

Commercially available aerosol nasal devices such as the LMA MAD device are not specifically engineered to facilitate nose-brain delivery, and consequently deposit most of the drug within the lower nasal cavity, resulting in suboptimal CNS penetration. Other problems associated with

traditional nasal sprays include variable aerosolized product, dependence on user position, and high frequency of device non-compliance/misuse. The POD device has specifically been developed to effectively and consistently deliver CNS therapeutics to the brain via the nasal/olfactory pathways. The device is not currently FDA approved, but numerous studies support its role in intranasal brain delivery of radiolabeled and therapeutic compounds.

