3.3 Exploratory Objectives

- To measure the effect of IN delivery of insulin glulisine on posterior parietotemporal and cingulate/precuneus glucose metabolism in subjects with aMCI and mild AD over a 6 month period.
- To measure the chronic effect of IN delivery of insulin glulisine on AD-specific cerebrospinal (CSF) biomarkers (A β 42, tau, and phosphotau) in subjects with aMCI and mild AD over a 6 month period.
- To measure the chronic effect of IN delivery of insulin glulisine on sleep (Sleep questionnaire and ESS) in subjects with aMCI and mild AD over a 6 month period
- To measure the chronic effect of IN delivery of insulin glulisine on olfaction in subjects with aMCI and mild AD over a 6 month period.

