7.2. Early Withdrawal

If subject withdraws from the study after the screening visit, but before visit 3, no further evaluations are necessary. If subject withdraws from the study after visit 3, all safety assessments will be performed (see section 7.3).

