12.2. Statistical Analysis of Efficacy Outcomes

Previous research has shown that the primary outcomes (ADAS-Cog 13, CDR-SOB, and FAQ) to be highly correlated. Therefore, to increase power and account for this correlation, the primary analysis will be a multivariate, linear mixed-effects regression. Specifically, the change in cognition and function measures between baseline and week 12 and between baseline and week 24 will serve as the primary outcome variables. We will include intervention arm, intervention week, intervention arm*week, age, and baseline test scores as fixed effects. The efficacy of intranasal (IN) insulin on cognition and function will be tested on the intervention arm*week interaction. Age and baseline test scores are included because of the possibility of unequal baseline values. Random intercept effects will be included to account for the nested structure of the data, multiple outcomes and observation points.

First, the assumptions of such a model will be verified. That is, the dependent variables will be tested for: (1) multivariate normality, (2) homoscedasticity, (3) equality of covariance matrices, and (4) independent observations. These outcome variables have been analyzed after log-transformation in previous studies because they have a distribution skewed to the right. We will confirm that this transformation is suitable for our study. If outcome variables are log-transformed, efficacy measures will correspond to percent change of cognitive outcomes.

To protect against type I error, efficacy of IN insulin will be considered if an overall cognitive decline is observed relative to placebo. Efficacy measures for composite cognitive and functional decline with corresponding 95% confidence intervals and p-values will be reported.

For the analysis of secondary cognition and function measures (Digit Span, Trailmaking, COWAT, Animal Naming, and WMS), secondary mood measure (GDS), and exploratory smell measure (AST) we will follow the same approach as for the primary outcomes. We have not included these tests as primary endpoints because they measure more specific effects of AD language, memory, mood, or olfaction impairment and, therefore, may be less sensitive to overall cognitive change in MCI/AD patients. Each outcome measure will be tested in its own linear mixed-effects regression model with measures from baseline to week 12 and baseline to week 24 as the outcome variables. The efficacy of IN

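### The smell test's nostril limit is never used and smell is not a safety outcome, so olfactory loss that a subject does not report need not appear in the safety results

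*Combined protocol and SAP*

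**What the plan says.** Section 1.1 gives two reasons for choosing glulisine. One is speculation that "zinc-containing compounds may be toxic to olfactory neurons"; glulisine contains no zinc. Section 2.1 says that the device delivers drug "via the olfactory and trigeminal neural pathways in the roof of the nasal cavity and olfactory nasal epithelium", and Section 5 sets dosing twice daily for 6 months.

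Section 7.4.12 describes the AST: "In 20 trials, the different scented markers are held up to the participants’ right or left nostril with their eyes closed". The subject chooses from eight scents, the maximum is 20, and the impairment limit is set by nostril: "A score of 2/10 or less in either nostril suggests impairment".

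Section 3.3 makes olfaction an exploratory objective. Section 12.2, on efficacy outcomes, says that for the "exploratory smell measure (AST) we will follow the same approach as for the primary outcomes". That means a linear mixed model of change to weeks 12 and 24, tested on arm by week.

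The safety endpoints in 4.2 are adverse events, vital signs and examinations, ECG and low glucose. Section 12.3 covers adverse event rates, vital signs and ECG. Neither names smell. The rule in 7.3 that a clinically significant change is recorded as an adverse event covers the assessments in that section; the AST is in 7.4. Table 2 places the AST at Visits 2, 7 and 10. It marks the GDS and C-SSRS at early withdrawal, but not the AST.

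**The concern.** The plan measures smell one nostril at a time, states what counts as impairment in a nostril, and then analyses only a mean. A mean of change on a 20-point total is a poor detector of one-sided loss in a few people. Subjects with cognitive impairment may not notice or report such a loss, and no AST result prompts an adverse event record.

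Two features add to this. The tested term is the interaction, which looks for an arm difference that changes between weeks 12 and 24, not for one present at both. And a subject who withdraws before Visit 7 or 10 may leave with no AST on treatment, which the mixed model treats as missing at random.

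At stake is a report of no effect on olfaction from an analysis that could not see individual loss, with nothing on smell in the safety tables beyond what subjects or investigators happened to raise.

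**Working it through.** The documents give no AST power, baseline or standard deviation, so there is no stated figure to reproduce. From the documents: 45 per arm, two-sided 0.05, eight scents, 20 trials. Ten trials per nostril is inferred from the 2/10 limit. Assumed: nostril baseline 4 to 8 out of 10; SD of change in the total 2 to 4.

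**1. Does the limit detect complete loss?** A nostril without smell guesses at 1/8, so its mean is 10/8 = 1.25. P(score of 2 or less) from binomial(10, 1/8) is 0.88. At both of two visits it is 0.88² = 0.78.

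**2. Effect on the mean.** If k of 45 treated subjects lose one nostril, the shift is (k/45) × (baseline − 1.25). Power is from the noncentral t, with the SD widened for the mixture of affected and unaffected subjects.

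- k = 3: (3/45) × 2.75 = 0.18 to (3/45) × 6.75 = 0.45 points; power 5.5% to 15%.
- k = 5: (5/45) × 2.75 = 0.31 to (5/45) × 6.75 = 0.75 points; power 6.5% to 29%.

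**3. The planned term.** With change as the outcome at two visits, the interaction is (arm difference at week 24) − (arm difference at week 12). A loss complete by week 12 and then stable gives d − d = 0. Simulated rejection was about 5% even with 9 of 45 affected.

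**4. Chance flags.** Let p be a nostril's true accuracy and q = P(2 or less of 10). A nostril must be above the limit at baseline to count as new. Nostrils and visits are taken as independent.

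- Single occurrence, per nostril: s = (1 − q) × [1 − (1 − q)²]; per subject: 1 − (1 − s)².
- Both visits, same nostril: b = (1 − q) × q²; per subject: 1 − (1 − b)².

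At p = 0.5, q = 0.0547. Then s = 0.945 × 0.106 = 0.1006, and 1 − 0.8994² = 0.191. Also b = 0.945 × 0.00299 = 0.0028, and 1 − 0.9972² = 0.0056.

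| True accuracy | Placebo flagged, single visit | Placebo flagged, both visits |
|---|---|---|
| 40% | 45% | 4.6% |
| 50% | 19% | 0.6% |
| 60% | 4.8% | 0.03% |

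**5. Illustrative comparison.** Suppose 20% of treated subjects lose one nostril completely by week 12, with p = 0.5. The expected active rates are 34% (single) and 15% (both). Enumerating the Fisher test with 45 per arm gives about 28% power for the single-occurrence rule and 62% for the both-visits rule. A simple test of the mean, with a shift of 0.20 × 3.75 = 0.75 points, has about 19%.

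**6. Small counts.** Fisher p is 0.24 for 3/45 against 0/45 and 0.026 for 6/45 against 0/45. With 0/45 observed, the one-sided 95% upper bound is 1 − 0.05^(1/45) = 6.4%.

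**The case against.** The strongest reply is that smell loss already has a route into the safety results. Section 11.1 makes any symptom that develops or worsens an adverse event, and 11.2.1 adds new abnormal findings that the investigator judges clinically significant. Adverse event rates are compared by arm. Reasons for withdrawal are documented, and withdrawn subjects are telephoned within 7 days (10.2). A subject who leaves because of a noticed smell problem has reported a symptom. Section 5.2 also continues follow-up, where possible, for those who only stop treatment. This stands. A reader might infer that smell loss could not appear in the safety results; the documents do not support that. The gap is loss that is not noticed or reported: no AST result triggers a record, and no smell-specific summary is planned.

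A reader might also infer that the protocol itself names smell loss as a harm of the nasal route. It does not. Section 1.1 ties olfactory toxicity to zinc, and choosing a zinc-free product is mitigation. Section 2.1 describes where drug is delivered, not toxicity.

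Third, a count at the 2/10 limit is not automatically better than a mean. At 40% accuracy a single-occurrence rule has about 8% power in the step 5 scenario, against about 13% for the mean. This also stands, and is why persistence is needed.

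Finally, the exploratory test is two-sided, so harm is not excluded in principle. That is true, but the test is insensitive to stable loss.

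**Conclusion.** The concern holds in this limited form. The nostril limit is unused, smell is outside 4.2 and 12.3, and there is no AST at early withdrawal. The planned mean analysis would very probably miss one-nostril loss in a few subjects, and the tested interaction would be almost blind to loss that is stable from week 12. Such loss need not appear in the safety results unless it is reported or judged clinically significant.

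The sizes depend on the assumed baseline and SD, on ten trials per nostril, on complete loss in one nostril, and on independent binomial scoring with constant accuracy. Extra visit-to-visit variation would change the chance-flag rates. None of this shows that glulisine or the device harms smell. Nor can one conclude that the DSMB would not see AST results, because its procedures are left to a charter outside these documents (13.2).

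This is a worthwhile, inexpensive improvement to safety reporting. Its main value is making individual cases visible: a handful will not reach significance, but a reader would see them.

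**What to change.** 1. Add to 4.2: new smell impairment, defined as an AST score of 2/10 or less in a nostril that was above 2/10 at baseline, present in the same nostril at both week 12 and week 24.
2. Tabulate single-visit occurrences separately, including those at early withdrawal. This covers loss first seen at week 24 and subjects who leave before both visits.
3. Add to 12.3 the count and proportion by arm, with an exact confidence interval for the difference, as a descriptive safety table. Show the number evaluable (above the limit at baseline).
4. Mark the AST in the Early Withdrawal column of Table 2, and confirm that the case report form holds each nostril's score as well as the total.
5. Keep the mean analysis as the exploratory objective.

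The cost is some wording, one table from data already scheduled, and one short test at an existing visit. The downside is some chance flags in subjects with low baseline scores, so results must be read against placebo. The both-visits rule also misses some true losses: about 22% of complete losses would score above the limit at one visit or the other (1 − 0.78). The single-visit table should pick up most of these.

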7.4.13 Sleep Questions

A set of 4 questions will be asked to the caregiver/spouse that looks at areas of sleep quality including sleep duration, sleep latency and sleep efficiency for the past month. The questions address the patient's usual bedtime and wake-up time, as well as how long it takes to fall asleep and how many hours of sleep are obtained per night. The caregiver will answer these questions for the subject.

7.4.14 Epworth Sleepiness Scale (ESS)

Epworth sleepiness scale (ESS) is a simple self-administered questionnaire that is widely used to measure the daytime sleepiness of an individual (52). It has 8 standardized questions that assess the likelihood of a subject dozing off or falling asleep (on a scale of 0-3) in daily living situations. A total of 0-24 score can be obtained. Excessive daytime sleepiness is assumed if a subject reaches a score of 10 and above. The caregiver will answer these questions for the subject.

7.5. Pharmacogenetics

APOE genotyping will be performed at Visit 1, following informed consent and will be used as part of the randomization. Sample will be tested at an external genetic processing facility, and results will be returned to testing site. The identity of study participants will be withheld from outsourced company completing testing. Samples will be identified by participant initials and a number identifier specific to this study.

8. INVESTIGATIONAL PRODUCT(S)

8.1. Description of Investigational Product

The Center for Memory and Aging will utilize the following investigational products:

- Intranasal delivery
- Insulin glulisine
- Placebo saline
- POD Device

8.2. Handling and Storage

The study drug (glulisine/saline) will be given to participant/care partner after training for administration.

The study drug on site will be kept per label recommendations and institutional Standard Operational Policy, specifically, but not limited to temperature controlled secure area.

Participants will be instructed to keep study drug at room temperature.

At investigational site, the study drug will be stored according to manufacturer recommendations. To ensure that a stable temperature and/or conditions are maintained, refrigerated study drug is electronically monitored for temperature control. . A log will be securely stored at the HealthPartners Center for Memory and Aging. Study staff will be responsible for safeguarding and maintaining the master log. In the event of a medical emergency requiring a blind break, unblinded study staff will be contacted by a member of the investigative team and the appropriate information will be relayed only to those responsible for patient's immediate medical care (e.g. ED physician).

8.3. Treatment Assignment

Randomization will be stratified by MOCA score (high = 23-27; low = 18-22), presence of non-insulin dependent diabetes, and APOE4 status *a priori* by the permuted block method. The trial is a double blinded study so that the subject, the investigator, and the trial coordinator will be unaware to which treatment group the subject has been randomized. To facilitate subject blinding, all subjects will undergo the same follow-up procedures. One investigative team member at the site will be unblinded to randomization and prepare the study dose for each subject. This person will not have responsibility for obtaining any study data. An electronic database will be used for automated randomization of participants using a table generated by the statistician.

8.4. Packaging and Labeling

Actual pharmacy-product indicator will be decided by pharmacy in order to maintain investigator objectivity.

All study drug and placebo will be labeled according to the following specifications:

- Protocol identifier/IRB approval/account/study number.
- Participant ID #.
- "Store at room temperature."
- "Last day to use" date."
- "Caution: New Drug--Limited by Federal (or United States) law to investigational use".
- Study contact # [contact].

8.5. Occupational Safety

No known significant safety risks exist to site personnel in direct or indirect contact with the study drug.

9. CONCOMITANT MEDICATIONS AND NON-DRUG THERAPIES

9.1. Permitted Medications

Any medication not listed in list of Prohibited/Conditional Medications will be permitted during this study. A record will be kept by site staff detailing doses and indication of any concomitant medications used by subjects.

Table 2: Prohibited Medications

Anticholinergics
Antihistamines (centrally-acting)
Barbiturates
Benzodiazepines
Insulin
Muscle relaxants
Neuroleptics
Opiates

9.2. Prohibited Medications

Subjects taking prohibited medications at time of screening will not be allowed to participate in study, unless such treatment is discontinued within 30 days. These medications include anticholinergics, and centrally acting antihistamines (e.g. Benadryl), opiates, benzodiazepines, barbiturates, neuroleptics, muscle relaxants, and insulin. For randomized subjects who take a prohibited med (episodic or PRN) will be considered for study continuation on an individual basis. Randomized subjects who take a prohibited med (long-term or for >7 days per concomitant illness/episode) will be withdrawn from study. Randomized subjects needing to initiate a conditional medication or alter dose of conditional medication during study will be considered on an individual basis.

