6.1.2. Exclusion Criteria

A subject will *not* be included for consideration in this study if any of the following criteria are met:

1. Subject has medical history and/or clinically determined evidence of other CNS disorders including, but not limited to brain tumor, active subdural hematoma, seizure disorder, multiple sclerosis, dementia with Lewy bodies, vascular dementia, corticobasal syndrome, progressive supranuclear palsy, Parkinson's disease, multiple system atrophy, frontotemporal dementia, normal pressure hydrocephalus, Huntington's disease, or Jakob-Creutzfeldt disease presenting as dementia.
2. Subject has medical history and/or clinically determined disorders: current B12 deficiency, chronic sinusitis or any untreated thyroid disease, significant head trauma, or history of difficulty with smell and/or taste prior to AD diagnosis.
3. Subject has history of any of the following: moderate to severe pulmonary disease, poorly

controlled congestive heart failure, significant cardiovascular and/or cerebrovascular events within previous 6 months, condition known to affect absorption, distribution, metabolism, or excretion of drugs such as any hepatic, renal or gastrointestinal disease or any other clinically relevant abnormality that inclusion, would pose a safety risk to the subject as determined by investigator.

4. Subject has had previous nasal and/or oto-pharyngeal surgery and severe deviated septum and/or other anomalies.
5. Subject has history of any psychiatric illness, with the exception of major depressive and anxiety disorder (according to DSM-IV TR) currently in remission or stable with treatment for ≥ 2 years, or any other psychiatric condition that inclusion would pose a safety risk to the subject as determined by investigator.
6. Subject is currently taking any medications, herbals and food supplements that are medically/clinically contraindicated as determined by investigator in order to comply with procedural testing of cognitive function as well as ensure study safety. See list of prohibited medications and compounds.
7. Subject has undergone a recent change (≤ 1 month) in their prescribed acetylcholinesterase inhibitor (e.g. donepezil, rivastigmine, galantamine) or memantine.
8. Subject has undergone a recent change (< 1 month) in their SSRI or anti-depressant medication.
9. Subject has current or recent drug or alcohol abuse or dependence as defined by DSM-IV TR.

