10. Screening laboratory results that are medically relevant, in which inclusion would pose a safety risk to the subject as determined by investigator.
11. The subject has participated in any other research study at least 3 months prior to
12. The subject has an insulin allergy.

1. Study assessments and procedures

A summary of study events and procedures is outlined in the Study Visit Table. Demographic, Screening, and Baseline Assessments are described in Sections 7.1.1-7.1.2, the Treatment Phase is outlined in Sections 7.1.3-7.1.10, and the Safety monitoring are detailed in Section 7.1.11; details of neuropsychological assessments are outlined in Section 7.4. Note that all visits are non-fasting unless otherwise noted.

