7.1. Demographic and Baseline Assessments

7.1.1. Visit 1; Screening Visit Fasting

The following procedures will be performed at this visit:

- Obtain written informed consent from study partner and subject (or subject's legally authorized representative) prior to any study related procedures.
- Collect laboratory samples for screening assessment, for specific tests refer to Table 1.
- Administer MOCA.
- Obtain Hachinski Score.
- Administer Geriatric Depression Scale (GDS).
- Review Inclusion/Exclusion Criteria.

- Review medical history, as it pertains to inclusion/exclusion criteria, such as research diagnosis, disease severity, and course of AD.
- Obtain subject's demographic information (date of birth, gender, race, education, etc.).
- Obtain details of medications taken over the course of the last 30 days.
- Complete physical exam, including neurological exam. Collect vital signs, height and weight prior to ECG and blood draw.
- Perform a standard 12-lead ECG.

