7.1.2. Visit 2; Baseline Visit

The following procedures will be performed at this visit:

- Review Inclusion/Exclusion Criteria.
- Collect vital signs and weight.
- Collect concomitant medication information and record AEs/SAEs.
- Neuropsychological testing with ADAS-Cog 13 and supplemental cognitive assessments.
- Administer CDR
- Administer Columbia-Suicide Severity Rating Scale (C-SSRS).
- Administer Functional Assessment Questionnaire (FAQ).
- Administer Alberta Smell Test.
- Administer sleep measures (Sleep questionnaire and ESS)
- Study Drug administration training.
- Hypoglycemia rescue training.
- Sub-study PET scan. For participating subjects, scan will be obtained within 1 week (\pm 3 days).
- Sub-study LP/ CSF. For participating subjects, procedure will be performed within 1 week (\pm 3 days).

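### The 30-day discontinuation option in Section 9.2 covers insulin, so, read as a deadline, it lets a diabetic stop therapeutic insulin to qualify for a trial meant for non-insulin dependent diabetics

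*Combined protocol and SAP*

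**What the plan says.** Section 9.2 sets the rule for anyone on a prohibited drug at entry: "Subjects taking prohibited medications at time of screening will not be allowed to participate in study, unless such treatment is discontinued within 30 days". The next sentence lists the drugs meant and ends with "opiates, benzodiazepines, barbiturates, neuroleptics, muscle relaxants, and insulin". The table in Section 9.1 gives the same eight classes, and neither place sets insulin apart from the rest.

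In Section 6.1.2, exclusion 6 reads "Subject is currently taking any medications, herbals and food supplements that are medically/clinically contraindicated as determined by investigator" and then refers to the prohibited list. Exclusion 3 ends with "any other clinically relevant abnormality that inclusion, would pose a safety risk to the subject as determined by investigator". Exclusion 10 covers "Screening laboratory results that are medically relevant, in which inclusion would pose a safety risk to the subject as determined by investigator". The only criterion that names insulin is exclusion 12: "The subject has an insulin allergy".

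The intended diabetic group is described elsewhere. Section 1.1 (rationale), Section 3.2 (secondary objective) and Section 8.3 (stratification) each refer to non-insulin dependent diabetes.

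**The concern.** Stopping a centrally acting antihistamine to enter a cognition trial is routine. Stopping therapeutic insulin is different, because the foreseeable result is a rise in glucose. Study drug cannot be assumed to replace it: 45 of the 90 subjects receive saline, and Section 1.1 argues that intranasal insulin has not been shown to lower peripheral glucose. The trial's glucose precautions point the other way. The one numeric limit is below 70 mg/dL (Sections 4.2 and 7.3.3), and the listed training is "Hypoglycemia rescue training".

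Two things are at stake. One is the safety of any subject who enters by this route. The other is agreement between who may enrol and the diabetic population that the protocol says it is studying.

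**Working it through.** The plan gives no figure to reproduce. The check compares the relevant sections.

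1. **Does the option reach insulin?** Yes. Section 9.2 states the option and then names the drugs it applies to. Insulin is one of 8 classes, with no carve-out.

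2. **What does the 30 days mean?** The sentence concerns people on the drug at the time of screening, so a deadline counted from screening is a natural reading. The alternative is a 30-day minimum washout. Section 5.2 caps screening plus baseline at 4 weeks, which is 4 × 7 = 28 days. A washout begun at screening would overrun that by 30 − 28 = 2 days. The text does not settle which is meant, and this point rests on the deadline reading only. Under that reading no minimum insulin-free period is stated.

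3. **Does another criterion close the route?** Exclusion 6 turns on current use, so stopping insulin satisfies its reference to the prohibited list. Exclusion 12 concerns allergy. None of the nine inclusion and twelve exclusion criteria names insulin-treated or insulin-dependent diabetes. Exclusions 3, 6 and 10 allow an investigator to refuse, but each depends on judgement. Criteria are reviewed at Visits 1, 2 and 3.

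4. **Does this differ from the stated population?** Sections 1.1, 3.2 and 8.3 all specify non-insulin dependent diabetes, but Section 6.1 never turns that into an eligibility rule. The prohibited list is the only explicit bar to an insulin user, and the 30-day option lifts it.

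5. **What would catch a problem?** From Table 1 and Sections 7.1.1 to 7.1.11:

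| Safeguard | When |
|---|---|
| Fasting metabolic panel (includes glucose) and HbA1c | Visit 1 |
| Fingerstick glucose before dosing and at 15 min, 30 min and 1 hour | Visits 3 and 4 (Weeks 0 and 1) |
| Metabolic panel | Visit 4 (Week 1), Visit 11 (Week 28), early withdrawal |
| Adverse event and medication review | Visits 2 to 11 |

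In addition, Section 9.2 requires withdrawal of a randomized subject who takes a prohibited drug long term or for more than 7 days. Sections 7.2 and 10.2 then call for the final safety assessments, and the early-withdrawal column of Table 1 includes the metabolic panel.

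6. **Context.** Between Week 1 and Week 28, 28 − 1 = 27 weeks, no glucose test is scheduled unless the subject withdraws early. That schedule applies to every diabetic in the trial. Section 9.2 does not create it, and correcting Section 9.2 does not change it.

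**The case against.** The best defence is that this is loose wording with several backstops. An investigator who saw a diabetic on insulin at Visit 1 would have fasting glucose and HbA1c in hand and could refuse under exclusions 3 or 10. Glucose is checked at Weeks 0 and 1, and Section 7.3.3 has the investigator told of any change from baseline, high or low. A subject who needs insulin again for more than 7 days must leave. Section 9.1 permits drugs that are not listed, and oral hypoglycemics are not listed, so stopping insulin need not mean untreated diabetes. A study partner attends all visits, and the data safety monitoring board includes an endocrinologist. Finally, the protocol does not define non-insulin dependent, so a type 2 diabetic who can safely stop insulin may arguably belong to the intended group.

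All of this stands, and it makes the point minor. It does not remove it: the rule as written offers stopping insulin as a way in, and only discretion prevents that before entry.

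A reader might go further and infer that Section 9.2 leaves subjects unmonitored for 27 weeks. The documents do not support that. The interval is a feature of the whole schedule, and the absence of a scheduled laboratory test is not the absence of surveillance, given the reviews at every visit from 2 to 11.

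**Conclusion.** The point holds as a minor defect. On the deadline reading, Section 9.2 allows an insulin-treated diabetic to stop insulin to qualify, which conflicts with the diabetic population named in Sections 1.1, 3.2 and 8.3 and is undesirable on safety grounds. The documents give no count of subjects affected, and it may be zero.

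The conclusion assumes that the 30 days run from screening and that no other operating document removes insulin from the option. It also takes insulin-treated diabetics to be outside the intended group in general, although the undefined term leaves room for exceptions.

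A reader might also infer misclassification in the diabetes stratum or harm to the efficacy comparison. Neither is supported. The protocol does not say how a site would classify such a subject, entry is decided under criteria common to both arms of a blinded randomized trial, and nothing here touches the primary model or the power calculation.

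**What to change.** Make two short changes in one amendment.

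1. In Section 9.2, add: *The 30-day discontinuation option does not apply to insulin.*
2. In Section 6.1.2 and the protocol summary, add the exclusion: *Ongoing insulin treatment for diabetes at screening. Brief in-hospital insulin use that has ended does not count.*

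The second sentence of the new exclusion matters because Visit 1 already includes this step: "Obtain details of medications taken over the course of the last 30 days". Excluding on any insulin in that history would turn away non-insulin dependent diabetics whom the trial wants, for example after a short admission. The same history lets the site apply the new criterion without collecting anything further.

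The cost is two lines of text and no new procedure. There may be a few fewer candidates, including a type 2 diabetic who could have stopped insulin safely. The change does not reach someone who had stopped insulin before screening, does not define how diabetes is established for the stratum, and leaves the glucose schedule as it is.
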